### 9.1 Safety Assessments

#### 9.1.1 Adverse Events

Definitions of AEs/SAEs, procedures for recording, evaluating, follow-up, and reporting of AEs/SAEs/pregnancy/overdose, as well as assessments of intensity and causality of AEs, are provided in Appendix 9.

Subjects with any Grade 3 solicited or unsolicited AEs are asked to immediately report these to the Investigator. Unscheduled visits will be performed when deemed necessary for safety assessments by the clinical Investigator and to ensure data integrity.

Since no control group is included in the trial, the subjects will serve as their own control for reactogenicity and safety assessments. For this purpose, the subjects will complete the pre-vaccination diary card on a daily basis as of Day -7 (i.e., during 1 week before the first vaccination) to give an indication of their normal life with co-morbidities. Solicited systemic AEs as well as unsolicited AEs will need to be collected similar to what is done during the 7 days after vaccination.

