10.7 Adverse Events (AEs)

Since no control group is included in the trial, the subjects will serve as their own control for reactogenicity and safety assessments. For this purpose, the subjects will complete the pre-vaccination diary card on a daily basis as of Day -7 (i.e., during 1 week before the first vaccination) to give an indication of their normal life with co-morbidities. Solicited systemic AEs as well as unsolicited AEs will need to be collected similar to what is done during the 7 days after vaccination.

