10.7.2 Solicited Adverse Events

Solicited systemic AEs (fever, headache, fatigue, chills, myalgia, arthralgia, nausea/vomiting, and diarrhea) will be recorded from Day -7 until Day -1 using a paper diary. These records shall provide a baseline for reactogenicity and safety for each enrolled subject. See Table 5.

Solicited local AEs (injection site pain, redness, swelling, and itching) and solicited systemic AEs will be recorded on the days of vaccination (Day 1 and Day 29) and the following 7 days using a paper diary. See Table 6.

Body temperature should be measured orally and by using the thermometer provided to the subject at Visit 1.

Solicited AEs will be assessed on an intensity scale of absent, mild, moderate, and severe (5 and 6). In case of related Grade 3 solicited or unsolicited AEs reported for more than 1 day in the diary, the subject will be questioned to establish the total duration of the AE as exactly as possible and this information will be recorded in the eCRF.

Solicited systemic Grade 3 AEs and unsolicited Grade 3 AEs, except for solicited injection site reactions, must be reported to the medical monitor without delay, on the same day of awareness by the site.

By definition, all solicited local AEs occurring from the time of first vaccination are considered related to trial vaccination. For solicited systemic AEs, the Investigator will assess the relationship between trial vaccine and each occurrence of each AE.

Table 5 Intensity Grading for Solicited Local Adverse Events

Adverse Event	Grade	Definition
Pain at injection site	0	Absent
	1	Does not interfere with activity
	2	Interferes with activity and/or repeated use of non-narcotic pain reliever >24 hours
	3	Prevents daily activity and/or repeated use of narcotic pain reliever
Redness	0	<2.5 cm
	1	2.5 – 5 cm
	2	5.1 – 10 cm
	3	>10 cm
Swelling	0	<2.5 cm
	1	2.5 – 5 cm and does not interfere with activity
	2	5.1 – 10 cm or interferes with activity
	3	>10 cm or prevents daily activity
Itching	0	Absent
	1	Mild, no interference with normal activity
	2	Moderate, some interference with normal activity
	3	Significant, prevents normal activity

Based on the United States Food and Drug Administration toxicity grading scale [5].

Table 6 Intensity Grading for Solicited Systemic Adverse Events

Adverse Event	Grade	Definition
Fever	0	<38°C
	1	≥38 – 38.4°C
	2	≥38.5 – 38.9°C
	3	≥39°C
Headache	0	Absent
	1	Mild, no interference with normal activity

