12.7 Analyses

The primary, secondary and exploratory endpoints will be analyzed overall, as well as per underlying comorbidity.

Based on the Protocol Amendment #1, a subset of analyses will be presented. See Section 6.1, 6.2, 6.3, 6.4 and Appendix 4 List of Abbreviated Scope Based on SAP Version 2.0 for additional details. Below all planned analyses according to SAP version 1.0 will be described. Any analysis not performed according to the abbreviated scope will be described.

Any analysis marked with an asterisk * will not be part of the abbreviated scope described in detail in Appendix 4.

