12.7.1.2 Analysis of Solicited AEs

The following summaries of solicited AEs within 7 days after each trial vaccination and within 7 days after any trial vaccination will be provided. If not stated otherwise the maximum grade will be presented (grade 0 to grade 3).

- Summary of solicited AEs, local AEs and systemic AEs, overall and by maximum grade
- Summary of local AEs, overall and by maximum grade
- Summary of systemic AEs, overall and by maximum grade (occurrence of systemic AEs will also be presented from day -7 until day -1)*
- Summary of related systemic AEs, overall and by maximum grade*
- Duration (days) of solicited AEs, overall and for Grade 3 events
- Duration (days) of local AEs, overall and for Grade 3 events*
- Duration (days) of systemic AEs, overall and for Grade 3 events*
- Duration (days) of related systemic AEs, overall and for Grade 3 events*
- Daily summary of local AEs (only for each dose)*
- Daily summary of systemic AEs (only for each dose)*
- Daily summary of related systemic AEs (only for each dose)*
- Summary of time of onset (Day) for grade 3 solicited AEs, any solicited AEs, local, systemic AEs, and related systemic AEs*
- Time of onset (Day) of local AEs*
- Time of onset (Day) of systemic AEs*
- Time of onset (Day) of related systemic AEs*
- Individual grade 3 solicited local and systemic adverse events will be presented in a figure.*

In addition, number and percentage of subjects with solicited Grade 3 adverse reaction(s) or SAEs considered as related to the trial vaccine according to the Investigator with the 95% credibility interval based on the Beta (0.5, 1.5) prior distribution will be calculated and summarized. This analysis is not part of the abbreviated scope.

Solicited AEs occurring on the day of vaccination and the following 7 days will be listed separately as well.

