14.3.2 Adverse Events Data Tables
Table 14.3.2.1.1 Overall Summary of Adverse Events (Safety Analysis Set)
Table 14.3.2.2.1 Summary of Solicited Adverse Events and Maximum Grade Occurring on the Day of Vaccination and the following 7 Days after any Dose (Safety Analysis Set)
Table 14.3.2.3.1 Local Solicited Adverse Events and Maximum Grade Occurring on the Day of Vaccination and the following 7 Days after any Dose (Safety Analysis Set)
Table 14.3.2.4.1 Systemic Solicited Adverse Events and Maximum Grade Occurring on the Day of Vaccination and the following 7 Days after any Dose (Safety Analysis Set)
Table 14.3.2.6.1 Duration of Solicited Adverse Events Occurring on the Day of Vaccination and the following 7 Days after any Dose (Safety Analysis Set)

Table 14.3.2.16.1 Unsolicited Adverse Events by System Organ Class and Preferred Term Occurring on the Day of Vaccination and the following 28 Days after any Dose (Safety Analysis Set)
Table 14.3.2.16.2 Unsolicited Adverse Events by System Organ Class and Preferred Term Occurring on the Day of Vaccination and the following 28 Days after Dose 1 (Safety Analysis Set)
Table 14.3.2.16.3 Unsolicited Adverse Events by System Organ Class and Preferred Term Occurring on the Day of Vaccination and the following 28 Days after Dose 2 (Safety Analysis Set)
Table 14.3.2.17.1 Unsolicited Adverse Events for Duration of Trial by System Organ Class and Preferred Term (Safety Analysis Set)
Table 14.3.2.17.2 Related Unsolicited Adverse Events for Duration of Trial by System Organ Class and Preferred Term (Safety Analysis Set)
Table 14.3.2.20.1 Unsolicited Adverse Events by System Organ Class, Preferred Term, and Maximum Severity Occurring on the Day of Vaccination and the following 28 Days after any Dose (Safety Analysis Set)
Table 14.3.2.20.2 Unsolicited Adverse Events by System Organ Class, Preferred Term, and Maximum Severity Occurring on the Day of Vaccination and the following 28 Days after Dose 1 (Safety Analysis Set)
Table 14.3.2.20.3 Unsolicited Adverse Events by System Organ Class, Preferred Term, and Maximum Severity Occurring on the Day of Vaccination and the following 28 Days after Dose 2 (Safety Analysis Set)
Table 14.3.2.26.1 Adverse Events of Special Interest for Duration of Trial by System Organ Class and Preferred Term (Safety Analysis Set)
Table 14.3.2.29.1 Adverse Events Leading to Study Withdrawal by System Organ Class and Preferred Term (Safety Analysis Set)

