Listing 16.2.4.1 Demographic and Baseline Data (Safety Analysis Set)
Listing 16.2.4.2 General Medical History (Safety Analysis Set)
Listing 16.2.4.3.1 Primary Co-Morbidities - Chronic Kidney Disease (Safety Analysis Set)
Listing 16.2.4.3.2 Primary Co-Morbidities – COPD (Safety Analysis Set)
Listing 16.2.4.3.3 Primary Co-Morbidities – Obesity (Safety Analysis Set)
Listing 16.2.4.3.4 Primary Co-Morbidities – Chronic Cardiovascular Disease (Safety Analysis Set)
Listing 16.2.4.3.5 Primary Co-Morbidities – Chronic HIV Infection (Safety Analysis Set)

Listing 16.2.4.3.6 Primary Co-Morbidities – Type 2 Diabetes Mellitus (Safety Analysis Set)
Listing 16.2.4.3.7 Primary Co-Morbidities – Subjects with a Renal Transplant (Safety Analysis Set)
Listing 16.2.4.4 Prior and Concomitant Medications (Safety Analysis Set)
Listing 16.2.4.5 Prior and Concomitant Vaccinations (Safety Analysis Set)
Listing 16.2.5.1 Administration of Investigational Product (Safety Analysis Set)
Listing 16.2.6.1 Vaccine-elicited IgG RBD Titers (Per Protocol Immunogenicity Set)
Listing 16.2.6.2 Vaccine-elicited IgG RBD Titers (Immunogenicity Set)
Listing 16.2.6.3 Virus Neutralizing Titers MN 25 TCID50 (Per Protocol Immunogenicity Set)
Listing 16.2.6.4 Virus Neutralizing Titers MN 25 TCID50 (Immunogenicity Set)
Listing 16.2.6.5 IgG NP Results (Immunogenicity Set)
Listing 16.2.6.7 Subjects with Virologically-Confirmed SARS-CoV2 infection as measured by RT-PCR (Safety Analysis Set)
Listing 16.2.6.8 Subjects with Asymptomatic SARS-CoV-2 Infection as measured with Retrospective Serology (Immunogenicity Set)
Listing 16.2.6.9 COVID-19 Symptoms (Safety Analysis Set)
Listing 16.2.7.1 Adverse Events (Safety Analysis Set)
Listing 16.2.7.2 Local Solicited Adverse Events (Safety Analysis Set)
Listing 16.2.7.3 Systemic Solicited Adverse Events (Safety Analysis Set)
Listing 16.2.7.4 Systemic Solicited Adverse Events 7 Days before Dose 1 (Safety Analysis Set)
Listing 16.2.7.5 Serious Adverse Events (Safety Analysis Set)
Listing 16.2.7.6 All Deaths (Safety Analysis Set)
Listing 16.2.8.1 Hematology Results and Change from Baseline (Safety Analysis Set)
Listing 16.2.8.2 Biochemistry Results and Change from Baseline (Safety Analysis Set)
Listing 16.2.8.3 Coagulation Results and Change from Baseline (Safety Analysis Set)
Listing 16.2.8.4 Pregnancy Test Results (Females of Childbearing Potential only) (Safety Analysis Set)
Listing 16.2.9 Vital Signs (Safety Analysis Set)

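### SAP v2.0 Appendix 4 titles no table for the pre-vaccination own-control diary or for vaccine-related solicited systemic AEs, so the retained systemic table cannot separate vaccine effect from background symptoms

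*SAP*

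**What the plan says.** **The own-control design.** SAP 10.7 states: "Since no control group is included in the trial, the subjects will serve as their own control for reactogenicity and safety assessments". Protocol 9.1.1 has the same arrangement and describes the daily diary from Day -7 as intended "to give an indication of their normal life with co-morbidities". SAP 10.7.2 says of the solicited systemic entries for Day -7 to Day -1: "These records shall provide a baseline for reactogenicity and safety for each enrolled subject".

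**Relationship to vaccine.** Protocol 4.2.1 includes relationship to vaccination in the primary endpoint for solicited systemic AEs, and the SAP 9.4 estimand repeats it. Protocol 10.3.5.1 requires the solicited AE tabulations to be repeated for systemic events judged related.

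**The reduced scope.** SAP 12.7 sets the rule: "Any analysis marked with an asterisk * will not be part of the abbreviated scope described in detail in Appendix 4". In SAP 12.7.1.2 the asterisk falls on "Summary of systemic AEs, overall and by maximum grade (occurrence of systemic AEs will also be presented from day -7 until day -1" and on "Summary of related systemic AEs, overall and by maximum grade". The related systemic duration, daily and onset summaries are starred too.

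**What Appendix 4 keeps.** For systemic solicited events it has "Table 14.3.2.4.1 Systemic Solicited Adverse Events and Maximum Grade Occurring on the Day of Vaccination and the following 7 Days after any Dose". For the pre-vaccination week it has only "Listing 16.2.7.4 Systemic Solicited Adverse Events 7 Days before Dose 1 (Safety Analysis Set").

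**The concern.** Several solicited systemic events, such as fatigue, headache, myalgia and arthralgia, may be present without any vaccine in people with COPD, heart failure, kidney disease or obesity. With no control arm, the plan has two ways to judge how much of the post-dose rate is background: the subject's own pre-vaccination week and the investigator's causality assessment. Neither appears in a titled table in the abbreviated scope.

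What is at stake is how the systemic part of the primary reactogenicity objective can be read. One component of a primary endpoint also has no titled table, although the protocol requires the tabulation.

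**Working it through.** The plan states no figure on this point, so the check is mainly a comparison of sections.

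**1. Required output against Appendix 4**

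| Item | Basis | SAP 12.7.1.2 | Appendix 4 |
|---|---|---|---|
| Systemic AEs after vaccination, any causality | Protocol 4.2.1, 10.3.5.1 | starred | Table 14.3.2.4.1 |
| Systemic AEs, Day -7 to Day -1 | SAP 10.7, 10.7.2 | starred (same line) | no table or figure; Listing 16.2.7.4 |
| Related systemic AEs | Protocol 4.2.1, 10.3.5.1; SAP 9.4 | starred | no table |

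The other solicited tables (14.3.2.2.1, 14.3.2.3.1, 14.3.2.6.1) also name only the vaccination day and the following 7 days. The overall AE summary in SAP 12.7.1.1 counts related unsolicited AEs, SAEs, medically attended AEs and AESIs, but has no row for related solicited systemic AEs. The analysis of Grade 3 reactions and related SAEs is dropped as well (SAP 6.4).

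**2. Do the asterisks agree with Appendix 4?** Not consistently. These starred items are retained:
- the systemic summary, as Table 14.3.2.4.1;
- related unsolicited AEs, as Table 14.3.2.17.2;
- unsolicited AEs by maximum severity, as Tables 14.3.2.20.1 to 14.3.2.20.3;
- the Grade 3 solicited figure, apparently as Figure 14.3.1.1.

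**3. Is a reason given?** SAP 6.4 gives reasons for dropping the Grade 3 credibility interval (small numbers) and CMI (invalid samples and small numbers). It names neither of the two omissions here.

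**4. Possible size.** The documents give no background rate, so the rate p in the 7-day baseline week is an assumption. The post-dose window is 8 days per dose (vaccination day plus 7), hence 2 × 8 = 16 days for a two-dose subject. Take no vaccine effect and two limiting cases:
- the same subjects report every week: the post-dose rate is p;
- constant daily risk and independent days: the rate over d days is 1 − (1 − p)^(d/7).

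| p (7 days) | Same subjects | Independent, 8 days | Independent, 16 days |
|---|---|---|---|
| 10% | 10% | 1 − 0.90^(8/7) = 11% | 1 − 0.90^(16/7) = 21% |
| 25% | 25% | 1 − 0.75^(8/7) = 28% | 1 − 0.75^(16/7) = 48% |
| 40% | 40% | 1 − 0.60^(8/7) = 44% | 1 − 0.60^(16/7) = 69% |

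Now add a vaccine effect. Let b be the background rate and a the vaccine-caused rate in one 7-day window, assumed independent. The observed rate is 1 − (1 − b)(1 − a), which exceeds a by b(1 − a). Over b = 10% to 50% and a = 30% to 70%, the excess runs from 0.10 × 0.30 = 3 points to 0.50 × 0.70 = 35 points. That is about 4 to 45 of the 129 enrolled subjects.

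**The case against.** The other side has real points.

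- **The asterisk is weak evidence.** The star on the systemic line is itself contradicted by Table 14.3.2.4.1, and the table shells are a separate document (SAP 10.0). A pre-vaccination column in that table cannot be ruled out. This stands as a caution, but the title names only the post-vaccination window, and the pre-vaccination week has its own listing and no table.
- **The reduction is disclosed in general terms.** SAP 6.3, 6.4, 9.4 and 12.7 all say that a subset will be presented. So the fault is the lack of an itemised reason, not concealment.
- **The data remain available.** The pre-vaccination and post-dose systemic events are both listed by subject, and with 129 subjects a reader could rebuild the comparison. That is true, but it leaves a basic analysis to the reader.
- **The baseline display was always modest.** Protocol 10.3.5.1 does not require a Day -7 to Day -1 table, and the fuller plan promised only a descriptive occurrence display. This stands; the protocol requirement applies to the related tabulation.
- **The trial is descriptive and stopped at 129 of 1,200.** This limits the severity.

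A reader might go further and infer that background symptoms will be reported as CVnCoV reactogenicity, or that every comparator and causality output is gone. The documents do not support that. The tables are titled as solicited adverse events, not reactions. Local reactions are related by definition. Laboratory and vital-sign changes from baseline stay planned, and related unsolicited AEs keep Table 14.3.2.17.2. Nor are 21%, 48% and 69% estimates of inflation: they need independent days and two complete diary windows, while chronic symptoms tend to recur in the same people.

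**Conclusion.** The point holds for solicited systemic AEs and should be fixed before the abbreviated report outputs are produced. It does not invalidate the trial.

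Three things are established from the text. No Appendix 4 table title covers the own-control week. None covers related solicited systemic AEs, despite the primary endpoint and Protocol 10.3.5.1. The asterisks and Appendix 4 disagree on scope, and SAP 6.4 gives no reason for either omission.

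On its title, the retained systemic table gives all-cause post-dose rates that cannot be separated from background symptoms. The size is unknown. With no vaccine effect, the baseline-week rate is the floor if the same subjects report each week; the rate is higher over 8 or 16 days if reports are spread across subjects. The conclusion assumes that the unseen table shells add nothing beyond the Appendix 4 titles.

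**What to change.** 1. Reconcile the asterisks in SAP 12.7.1.1 and 12.7.1.2 with Appendix 4, and state in SAP 6.4 the reason for any output still omitted.
2. Add to Appendix 4 one table of systemic solicited AEs by maximum grade with columns for Day -7 to Day -1, after dose 1 and after dose 2, overall and by co-morbidity. Show the number of subjects with diary data in each column. Keep the endpoint window (vaccination day plus 7 days) and footnote that it is 8 days against 7, or add an equal 7-day window as a supplementary comparison.
3. Restore the summary of related solicited systemic AEs by maximum grade.
4. Optional: count the subjects whose post-dose maximum grade exceeds their own pre-vaccination maximum. This goes beyond the existing plan but uses the own-control design directly.

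The cost is SAP wording and one or two descriptive tables, with no new data collection. The downside is a slightly larger abbreviated report, with small counts in the co-morbidity columns.

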12.7.2 Primary and secondary Humoral Immune Response Endpoints

The primary humoral response endpoints will be analyzed with the per protocol immunogenicity subset population. The primary endpoint is subjects with seroconversion on day 43 compared to baseline (Day 1); the time points day 29, day 120 will be presented for the per protocol immunogenicity subset population as well. Seroconversion is defined as an increase above 1 from baseline (Day 1) (see Section 10.8.1), In addition conversion over 2 fold and 4 fold will be presented. Analysis based on the immunogenicity set will not be presented according to the abbreviated scope.

The following tables will be presented for SARS-CoV-2 S (RBD) protein antibodies, as measured by ELISA and SARS-CoV-2 neutralizing antibodies, as measured by an activity assay:

- The estimate and 95%-credibility intervals and proportion and Clopper-Pearson exact confidence intervals will be presented as well for seroconverted subjects.
- Geometric mean (GM), geometric standard deviation (GSD) and 95%- confidence intervals as well as fold change from baseline.

In addition, the following figures will be presented for the time points day 29, day 43, day 120, and for the per protocol immunogenicity population and immunogenicity set:

- Fold change from baseline for Individual subjects by co-morbidity presented in a line plot.
- Mean fold change from baseline by co-morbidity
- Individual line plots of GMTs by co-morbidity
- Line plot of GMTs with geometric mean and confidence intervals by co-morbidity
- Boxplots with median, Q1 and Q3, and whiskers representing minimum and maximum.

SARS-CoV-2 S (RBD) protein antibodies, and SARS-CoV-2 neutralizing antibodies results will be listed as well.

12.7.3 Exploratory Endpoints

The below mentioned exploratory endpoints will be included in the abbreviated scope. Cell-mediated immune response and cytokine concentrations will not be included.

- Number of subjects and percentages with RT-PCR-confirmed SARS-CoV-2 infection at clinically determined time points throughout the trial will be tabulated by time point. This table and listing will be presented for the safety set.
- Number of subjects and percentages with asymptomatic SARS-CoV-2 infection as measured by serological titers of nucleocapsid antibodies on day 1, day 43 and day 120 will be tabulated by time point. Subjects with COVID-19 symptoms are excluded.

12.7.4 Laboratory Data

Blood samples for determination of hematology, clinical biochemistry and coagulation will be analyzed at each trial visit they are collected by co-morbidity for SAS. In case of abnormal results additional analyses will take place.

All laboratory data will be summarized in International System (SI) units. The conversion factors from conventional to SI units will be documented in the Local Lab Conventions document for this trial.

Laboratory data will be graded according with the United States Food and Drug Administration (FDA) toxicity grading scale [5].

All laboratory data will be listed.

12.7.4.1 Hematology

Hematology parameters include Leukocytes (WBC), Erythrocytes (RBC), Hemoglobin, Hematocrit, Ery. Mean Corpuscular Hemoglobin (MCH), Ery. Mean Corpuscular HBG Concentration (MCHC), Ery. Mean Corpuscular Volume (MCV), Platelets, Neutrophils (Absolute), Lymphocytes (Absolute), Monocytes (Absolute), Eosinophils (Absolute), Basophils (Absolute), Reticulocytes (Absolute), Neutrophils/Leukocytes (%), Lymphocytes/Leukocytes (%), Monocytes/Leukocytes (%), Eosinophils/Leukocytes (%), Basophils/Leukocytes (%), Reticulocytes/Erythrocytes (%).

Hematology parameters will be summarized (n, mean, SD, median, Q1, Q3, minimum and maximum), including change from baseline at each visit. In addition, shift tables summarizing the shift including baseline, minimum and maximum post baseline values and last value will be presented. In addition, all parameters will be presented in a line plot for all planned visits.

